11.10 Publication and Dissemination policy	60
12. REFERENCES	62
SIGNATURE PAGE 1 (Chief Investigator)	64
SIGNATURE PAGE 2 (Sponsor)	65

Short Title:	Protocol No:	Sponsor:	Version: 5.0
IP4 - CHRONOS	19CX5006	Imperial College London	Date:
			13 th July 2022

SIGNATURE PAGE 3 (Statistician)66	
SIGNATURE PAGE 4 (Principal Investigator)67	

TRIAL SUMMARY

TITLE	Comparative Health Research Outcomes of NOvel Surgery in prostate cancer			
AIM	To deliver an overarching RCT framework to efficiently evaluate novel surgical techniques in the treatment of non-metastatic prostate cancer			
	CHRONOS-A Pilot: To determine if men will agree to participate in an RCT that randomly assigns them to focal therapy alone or radical therapy (radiotherapy or prostatectomy).			
	Main: To determine if focal therapy alone is non-inferior when compared to radical therapy (radiotherapy or surgery) in terms of progression-free survival (PFS) at 5 years in men with clinically significant non-metastatic cancer.			
	CHRONOS-B Pilot: To determine if men expressing a preference for focal therapy will agree to participate in a multi-arm, multi-stage (MAMS) RCT that randomly assigns them to focal therapy alone or focal therapy in combination with neoadjuvant and/or adjuvant agents.			
	Main: To determine if focal therapy combined with neoadjuvant and/or adjuvant agents, compared to focal therapy alone, will improve failure-free survival (FFS) at 5 years, in men with clinically significant non-metastatic cancer			
PHASE	Phase II Randomised Control Trial (RCT) incorporating an internal pilot			
DURATION	Pilot: Recruitment 12 months. Minimum 3 months follow-up. Total 15 months. Main study: Recruitment further 48 months. Total including follow-up = 96 months			
DESIGN	Randomised controlled trial Two linked RCTs with CHRONOS-A and CHRONOS-B discussed with patients and choice of A or B dependent on physician and patient equipoise.			
	- CHRONOS-A Two arm RCT			
	- CHRONOS-B Multi-Arm Multi-Stage (MAMS) Randomised Control Trial			

Short Title: IP4 - CHRONOS	Protocol No: 19CX5006	Sponsor: Imperial College London	Version: 5.0 Date: 13 th July 2022
			10 daily 2022

SAMPLE SIZE	Eggeihility/nilot		
SAIVIPLE SIZE	Feasibility/pilot		
	CHRONOS-A 60 patients over 12-months (These participants will form part of the main study if feasibility is met and funding obtained)		
	CHRONOS-B 60 patients over 12-months (These participants will form part of the main study if feasibility is met and funding obtained)		

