2.7 Summary Table of Objectives and Endpoints

Protocol No: 19CX5006 v5.0 13th July 2022

Short Title:	Protocol No:	Sponsor:	Version: 5.0
IP4 - CHRONOS	19CX5006	Imperial College London	Date:
			13 th July 2022

Study stage	Objectives	Endpoints	Time-point(s) of evaluation of this endpoint (if applicable)
Pilot	Primary	As above	At time of consent (acceptance to randomisation) and at time to treatment (compliance)
Pilot	Secondary	As above	At time of consultation for study, after consent and after treatment with a minimum follow-up of 3 months after randomisation
Main (if funded)	Primary	As above	At time of progression or failure judged clinically or maximum 5 years follow-up after randomisation
Main (if funded)	Secondary	As above	Up to and including 5 years from randomisation

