5.7 Visit Schedule

The design and number of visits mirror the standard of care pathway for patients undergoing either focal therapy or radical therapy, so that additional patient burden is minimal. Prior to enrolment, all patients will have undergone a Prostate Specific Antigen (PSA) blood test, a diagnostic prostate MRI and prostate biopsies. A standard of care (SOC) multi-disciplinary team case review will precede any discussion with the patient on all suitable treatment options and trial suitability. After an MDT discussion confirming suitability for FT and/or radical therapy has taken place, a patient information sheet (PIS) explaining the study will be provided, after which patients will be given a minimum of 24 hours to consider taking part. We aim for consent to be taken during a SOC appointment, or an additional consultation via phone, or in person. Randomisation will take place during the visit in which consent is taken along with any required neoadjuvant therapy, as allocated via randomisation, to be prescribed and within 24 hours of receiving the prescription. Time from randomisation will be used to define progression free survival and failure free survival. The end of treatment is defined as the final part of any intervention. For radiotherapy, this is the final radiation fraction completed and for prostatectomy and focal therapy the point at which the catheter is removed. Therefore, the follow-up visits noted below will start from these time-points, which will define the date of first follow-up visit (visit 2).

Protocol No: 19CX5006 v5.0 13th July 2022

IP4 - CHRONOS 19CX5006 Imperial College London Date: 13 th July 2022

Visit Schedule:

	Screening & Consent	Visit						
Visit	1	2	3	4	5	6	7	6 monthly visits until last visit 60 months after visit 2
Months		These below specify the months after the completion of each treatment in each arm						
		0	3	12	18	24	30	31-60. Visits 4 onwards can be telephone consultations in order t note clinical outcomes although MRI scans and biopsies where done will require physical visits to the hospital
Informed Consent and enrolment into either CHRONOS A or CHRONOS B	Х							
Inclusion & exclusion criteria checked, including concomitant medication review	Х							
Randomisation	Х							
Prescription of neo- adjuvant therapy	X (if randomised to such arm)							Within 24hrs of randomisation
PSA blood test	Such anny		Х	Х	Х	Х	Х	X (6 monthly)

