 Arm 1 (Control arm): Focal therapy alone (high intensity focused ultrasound [HIFU] or cryotherapy or other validated energy modality as per physician and centre choice). A second treatment in-field, or a first focal ablation to an out-of-field progressive or de novo lesion will be allowed but will be regarded as failure events for the purpose of CHRONOS-B. Cryotherapy can be used after HIFU and HIFU can be used after

Short Title: IP4 - CHRONOS	Protocol No: 19CX5006	Sponsor: Imperial College London	Version: 5.0 Date: 13 th July 2022
			10 daily 2022

cryotherapy. Where patients have undergone hemiablation to one lobe and then undergo hemiablation of the contralateral lobe will be designated as failure of focal therapy

- Arm 2 (Intervention arm): Neoadjuvant finasteride 5mg once daily for a minimum of 12 weeks (84 days) followed by focal therapy (as per control arm).
- Arm 3 (Intervention arm): Neoadjuvant bicalutamide 50mg once daily therapy for 12 weeks (84 days) followed by focal therapy (as per control arm).

Other arms can be added in future with protocol amendments.

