5.9 Follow-up

Follow-up will consist of serum Prostate Specific Antigen (PSA) tests at 3 months and 12 months after completion of treatment as defined above. Thereafter, PSA will be measured 6-monthly until a progression event is determined, for 5 years after initial randomisation or mortality (whichever is first).

Patient reported outcome measures (PROMs) will be collected at 3 and 12 months and then annually thereafter until progression, mortality or 5 years after initial randomisation (whichever is first). The minimum follow-up for each patient will be 5 years in the main study although yearly follow-up will continue long term in clinical standard care through linkage to national databases.

NB: if the trial does not proceed to the Main Stage following the analysis of the Pilot, patients will be followed up for a minimum of 3 months and will then revert to standard of care in which the clinical care provided to patients will not differ from the clinical follow-up stipulated in this protocol. At the end of the study patients will continue to be followed up locally within their recruitment centres within the ICE (European Registry for Cryosurgical Ablation of the prostate, EuCAP) or the HEAT international HIFU registry as per NICE guidelines IPG432/IPG42.

Patient reported outcome measures

The EORTC QLQ-C30 with the prostate-specific module, International Prostatic Symptoms Score (IPSS), EPIC bowel and bladder and International Index of Erectile Function 15 (IIEF15) will be used.

The EuroQol (EQ-5D) will be used in the study as a generic measure of health-related quality-of-life which can be linked to public preferences. These data will be used to calculate quality-adjusted life-years as part of a future health economic evaluation. Patients agreeing to return questionnaires on quality of life should continue to complete quality of life data for 5 years after randomisation. Questionnaires should be self-administered, although it is recommended that a key person (e.g. research nurse) at each centre be responsible for the data collection to optimise compliance and completeness of the data.

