8. STATISTICAL ANALYSES

8.1 Sample Size and power considerations

8.1.1 Feasibility and Pilot Stage

For both CHRONOS-A and CHRONOS-B feasibility is considered in terms of recruitment rate, the acceptability of the trial randomisation and adherence to arm allocation.

- CHRONOS-A: A two-arm RCT will recruit 1190 patients over a total recruitment and follow-up period of 8 years. The number and nature of centres involved would require between 1-2 patients recruited per-centre per-month. At a conservative rate, we expect to recruit 60 patients in the Pilot Stage in 6 centres over 12-months.
- CHRONOS-B: A three-arm* MAMS RCT 1260 patients to be recruited over five years at a rate of 20 patients per month. The number and nature of centres involved would require between 1-2 patients recruited per-centre per-month. Conservatively, we expect to recruit 60 patients in the Pilot Stage in 6 centres over 12-months.

Short Title: IP4 - CHRONOS	Protocol No: 19CX5006	Sponsor: Imperial College London	Version: 5.0 Date: 13 th July 2022
			10 Gary 2022

^{*}Further arms may be added via substantial amendments

N.B. Patients observed in the Pilot Stage will be included in the Main Stage. In the event that the study does not proceed from Pilot to Main, patients recruited into the Pilot will be followed up for 6 months for safety monitoring.

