5.1. Primary Outcome Measures

Feasibility of recruitment, acceptance of randomisation and compliance to allocated arm.

- Recruitment is defined as total number of patients recruited (consented) out of the total number of patients approached.
- Randomisation is defined as the total number of patients randomised out of the total number of patients recruited (consented).
- Compliance comprises of treatment compliance (CHRONOS-A and CHRONOS-B) and drug compliance (CHRONOS-B):
 - o Treatment compliance (CHRONOS-A and CHRONOS-B):
 - Proportion of patients who underwent treatment (Focal therapy ((CHRONOS-A and CHRONOS-B)), Radiotherapy/Brachytherapy or Prostatectomy (CHRONOS-A)) as recorded by date of treatment and completed treatment details recorded at Visit 2/3 (treatment visit)
 - o Drug compliance (CHRONOS-B). This will be measured in two ways:
 - Proportion of patients who returned their empty blister pack (yes/no), as recorded at Visit 3.
 - Proportion of patients who were given the drug (recorded at Visit 2) and who did not have a registered protocol deviation (stating that the drug was taken for less than 8 weeks).

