Biopsy				X (focal therapy arms)				
Treatment		X (these vary in length)						X (focal therapy arms – a second treatment will be permitted for a histologically confirmed recurrent, residual or new out-of-field disease)
Clinical assessment (optional, only if required)			Х	Х	х	х	Х	
PROMS questionnaires	Х		х	х		х		X (every 12 months, at 24, 36, 48 and 60 months visits)

Imperial Clinical Trials Unit	STATISTICAL ANALYSIS PLAN: FEASIBILITY	CHRONOS
----------------------------------	--	---------

[figure not shown]
Review/ reporting of patient AEs/SAEs		Х	Х	Х	Х	Х	Х	Х
Blood and urine tests including those for biobanking (optional)	Х		Х	Х				X

Time window for each visit will be +/- 4 weeks

Minimum length of follow up for the pilot will be 3 months from treatment for each patient. Then treatment will revert to standard of care.

[figure not shown]

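### Pilot follow-up has conflicting lengths and start points, and the stated 15-month pilot fits only a 3-month clock that starts at randomisation

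*Protocol*

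**What the plan says.** Four statements govern how long pilot patients are followed:

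- Protocol 2.7, secondary pilot endpoints: "with a minimum follow-up of 3 months after randomisation".
- SAP 6.7.2, below the visit table: "Minimum length of follow up for the pilot will be 3 months from treatment for each patient".
- Protocol 8.1.1, if the study stops after the pilot: "patients recruited into the Pilot will be followed up for 6 months for safety monitoring". No start point is given.
- Protocol 5.9, for the same contingency: "patients will be followed up for a minimum of 3 months and will then revert to standard of care". SAP 6.6.2 and SAP 11 repeat this. Again no start point is given.

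The Trial Summary states the length of the pilot: "Pilot: Recruitment 12 months. Minimum 3 months follow-up. Total 15 months".

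The visit clock is set in Protocol 5.7. Treatment ends at the last radiotherapy fraction or at catheter removal. "Therefore, the follow-up visits noted below will start from these time-points", which makes Visit 2 month 0 and Visit 3 month 3. In CHRONOS-B both drug arms take 84 days of drug before ablation. For Arm 2, Protocol 5.8 says "Neoadjuvant finasteride 5mg once daily for a minimum of 12 weeks (84 days) followed by focal therapy".

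The SAP uses Visit 3 in its results. SAP 10.4 makes it the last follow-up visit of the feasibility phase, and the footnotes to SAP Tables 2.6 and 2.7 expect patients to be there before that phase closes. SAP 5.1 defines one drug-compliance measure as "Proportion of patients who returned their empty blister pack (yes/no), as recorded at Visit 3".

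**The concern.** The length and the start of the follow-up window both change from place to place. A site reading Protocol 8.1.1 would monitor safety for 6 months if the trial stopped after the pilot. A site reading 5.9 could hand the patient back to routine care after 3. Adverse events by arm are part of the SAP's primary pilot analysis (SAP 9.3 and 9.8), so the window affects a reported result.

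The stated pilot length also does not deliver the SAP's own follow-up rule. Men who enter a drug arm late cannot have three months of post-treatment follow-up by month 15. The 3-month questionnaires (SAP 9.4) and possibly one drug-compliance measure would then be missing for a reason unrelated to tolerability or adherence. The SAP analyses randomised patients by intention to treat (SAP 7) and provides no missing-data method for the pilot (SAP 9.6). It gives no rule for a man whose visit is not yet due.

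**Working it through.** **The plan's figure.** A man randomised at the end of month 12 and followed for 3 months from randomisation finishes at 12 + 3 = 15 months. The stated total is reproduced.

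**The SAP rule.** Inputs: 84 days of drug (Protocol 5.8); Visit 3 at 3 months after treatment, with a window of 4 weeks either way (Protocol 5.7, SAP 6.7.2); one month = 365.25/12 = 30.44 days. Then 84 days = 2.76 months and 4 weeks = 0.92 months. Time from randomisation to Visit 3 is T = 2.76 + wait for focal therapy + 3, and the last man arrives at 12 + T.

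- No wait: T = 5.76; last man at 17.76 months.
- No wait, early edge of the window: T = 5.76 − 0.92 = 4.84; 16.84 months.
- Assumed 4-week wait: T = 5.76 + 0.92 = 6.68; 18.68 months.

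**The 6-month rule.** From randomisation: 12 + 6 = 18.0 months. From treatment in a drug arm: 12 + 2.76 + 6 = 20.76 months.

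**Men without Visit 3 if data were cut at month 15.** Assume uniform accrual over 12 months and 40 drug-arm men (20 per arm, Protocol 3.2). The share not yet there is (12 + T − 15)/12 = (T − 3)/12.

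- No wait: 2.76/12 = 23%, about 9 men.
- Early edge: 1.84/12 = 15%, about 6 men.
- 4-week wait: 3.68/12 = 31%, about 12 men.

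**Effect on the drug-compliance criterion, if Visit 3 is the 3-month visit.** SAP 9.3 applies its thresholds to the lower end of the confidence interval: 90% or more is viable, 80-90% needs remedial work, and below 80% goes to the TSC. Pooling both drug arms, exact (Clopper-Pearson) lower 95% limits are:

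- All 40 assessed and compliant, 40/40: 91.2%.
- Nine not reached and scored non-compliant, 31/40: 61.6% (Wilson 62.5%).
- Nine not reached and excluded, the rest all compliant, 31/31: 88.8% (Wilson 89.0%).
- Six not reached and excluded, the rest all compliant, 34/34: 89.7% (Wilson 89.9%).

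The SAP names no interval method for these proportions. Its recruitment interval in section 11 matches the normal approximation: 0.33 ± 1.96 × √(0.33 × 0.67/60) = 0.211 to 0.449. By that formula 31/40 gives 0.775 − 1.96 × √(0.775 × 0.225/40) = 64.6%, still below 80%. At 31/31 it gives an interval of zero width, so the 88.8% result depends on using an exact or score interval.

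The SAP also evaluates each arm separately. There, 20/20 gives an exact lower limit of 83.2%, so a single arm cannot reach 90% on that interval even with complete follow-up. Timing could change only the pooled result from viable to not viable.

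**If Visit 3 instead means the focal therapy visit.** The last man reaches it at 12 + 2.76 = 14.76 months, about 7 days inside month 15. With a 4-week wait it is 15.68 months, and 0.68/12 = 6%, about 2 of 40, would be late.

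**The case against.** Several stronger readings are tempting, and the documents do not support them.

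- **That 15 months is an arithmetic error.** It is not: 12 + 3 = 15 is right under Protocol 2.7. It fails only when the SAP's start point is applied, so this is a conflict between passages.
- **That unreached men will depress compliance.** Nothing fixes a data cut-off at month 15, and nothing says such men are scored non-compliant. The Trial Summary gives a planning duration with a minimum follow-up, and the SAP expects Visit 3 data before the pilot closes.
- **That compliance is recorded at Visit 3.** SAP 5.1 and 9.3 put blister-pack return there, but SAP 8.3 lists it as collected at Visit 2, and Protocol 6.4 prefers return at the focal therapy visit. SAP 5.1 describes the treatment visit as Visit 2 or 3. The second drug-compliance definition rests on drug given and the absence of a deviation for less than 8 weeks of drug, so it does not need Visit 3.
- **That 69-77% compliance would breach the 80% floor.** Those are the largest possible point proportions when 31% or 23% of men are unreached. SAP 9.3 applies the threshold to the lower confidence limit, and a result below it goes to the TSC for decision rather than failing automatically.
- **That a clock from randomisation yields no safety data after ablation.** It leaves about a week after the drug course (3 − 2.76 = 0.24 months), and this concerns the two drug arms only. The row in Protocol 2.7 covers secondary pilot endpoints. Adverse events are reviewed from Visit 2 onward and recorded throughout the trial (SAP 9.3).

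It can also be said that 6 months satisfies a minimum of 3, so those two statements are not strictly exclusive. That is true, but one commits to 6 months of safety monitoring and the other permits return to routine care earlier. The recruitment-based progression rule in SAP 11 is unaffected. What stands is the conflict over duration and start point, and a stated pilot length that cannot meet the SAP's rule in the drug arms.

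**Conclusion.** The point holds as an inconsistency with a practical consequence. The follow-up statements cannot all be applied. Under the SAP's rule and visit schedule, the 15-month pilot is about 2.8 months short for the last drug-arm man with no wait (17.8 − 15), 1.8 months short at the early edge of the window, and 3.7 months short with a 4-week wait. That follows from the documents' own figures, apart from the assumed wait.

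The 15-31% of drug-arm men without Visit 3 and the 3-month questionnaires is conditional on a cut at month 15 and on uniform accrual. The compliance limits of 61.6% and 88.8%, against 91.2% for 40/40, carry further conditions: that blister packs are recorded at the 3-month visit, that unreached men are handled as described, and, for 88.8%, the choice of interval. They show how far an unstated rule could move a progression measure and do not predict the pilot's result.

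**What to change.** 1. Reconcile the Trial Summary, Protocol 2.7, 5.9 and 8.1.1, and SAP 6.6.2, 6.7.2 and 11 to one pilot follow-up duration with one start point. Which duration and start point is for the sponsor to decide.
2. Restate the pilot total and specify a data cut-off, both following from that rule.
3. Name one visit at which drug compliance and treatment compliance are recorded, and align Protocol 6.4, SAP 5.1, 8.3 and 9.3, and the footnotes to SAP Tables 2.8 to 2.10.
4. Set the cut-off so that every randomised man can reach that visit, or restrict the denominator to men due for it. Restriction alone reduces precision: at 31/31 the pooled exact limit is already below 90%.

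The cost is wording, and possibly a longer stated pilot: about 2 to 4 months more under the SAP's rule, 3 months more if 6 months is counted from randomisation, and 5.8 months more (20.8 − 15) if it is counted from treatment in the drug arms.

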8.1.2 Main study

Sample size calculations below are for the full phase II studies based on progression-free survival (PFS):

CHRONOS-A: Progression-free survival (PFS) in our population at 5-years is approximately 85-90% after radiotherapy and similar for prostatectomy. Overall survival is high and being a 10-15 year outcome it will not be used in this study. PFS is a clinically meaningful endpoint, with precedence in other studies and can be measured in the same way in both arms (time to salvage therapies). Our hypothesis is that FT is non-inferior in terms of PFS, whilst having fewer side-effects. The question is what margin of non-inferiority should be in the main study. In the CHHIP radiotherapy RCT a 20% relative change was acceptable as a non-inferiority margin comparing one form of radiotherapy to another form of radiotherapy HR 1.208; absolute difference 5%). In the PART RCT pilot (prostatectomy versus FT), a failure of 25% (PFS 75%) for surgery compared to a maximum 35% after focal (PFS 65%) was accepted by the NIHR-HTA as a non-inferior design because the functional detriment would be substantially better.

For a patients' perspective, we can look at the unpublished NCRN COMPARE study (presented at NCRI UK Annual Conference, November 2018). This was a discrete choice experiment where 544 newly diagnosed men (~30 UK centres) were asked to make choices between different treatment scenarios. Marginal Rate of Substitution (MRS) were calculated (trade-offs men are willing to make between side-effects and survival). On average men are willing to trade 0.68% of survival chance against 1% chance of improving urinary function, with PFS and sexual function MRS at 0.41% and 0.28%. Based on the above, it is reasonable to assume 85% PFS after radiotherapy with a non-inferiority margin of 5% for FT would meet clinical and patient acceptance.

Based on an allocation ratio of 1:1 and a non-inferiority margin of 0.05 with a 0.85 PFS rate in the standard care arm (at median 5-years), power 0.80 and alpha 0.05, drop-out after randomisation of 5%, the overall required sample size is 1190 with 136 expected total number of events. Total recruitment and follow-up period will be 8 years. If recruitment rates were deemed to be high then the power could be adjusted to 0.90 and the total sample size will be 1660 with 189 expected total number of events. This will be on the advisement of the TSC. PFS for the main Stage will be defined as transition to salvage therapies or metastases or mortality related to prostate cancer.

CHRONOS-B main stages II and III: Using the latest update of –nstage-, with an allocation ratio of 1:1:1, we anticipate approximately 1200 patients are required over 5 years to observe 120 control arm failure-free survival (FFS) events within 7.6 years. This time will be dependent on observed FFS event rates and is based on an assumption of 20 patients recruited per month. This calculation gives 85% power at the efficacy stage analysis, to detect a hazard ratio (HR) of 0.67 and is based on 20% of patients having a FFS event by 3 years (30% by 5-years).

Table 1. Sample size calculations

	Short Title: IP4 - CHRONOS	Protocol No: 19CX5006	Sponsor: Imperial College London	Version: 5.0 Date: 13 th July 2022
١				10 Gary Lore

	Stage 1	Stage 2	Overall
Alpha	0.45	0.025	0.044
Power	95%	85%	83%
Critical HR (guidance for stopping early)	0.974		-
Control Arm Events	47	120	-
Accrual	20pts/m	20pts/m	20pts/m
Cumulative Patients	1003	1200	-
Time to analysis (years)	3.4	4.2	7.6

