8.2 Planned recruitment rate

Within the UK approximately 10,000 patients meeting our eligibility criteria undergo radical therapy a year and 700 patients undergo FT. Thus, the potential pool of eligible patients is large and the timeline to full accrual is based on UK estimates and would allow both CHRONOS-A and CHRONOS-B to complete recruitment within 5 years and primary outcome analysis to occur after 8 years. For the pilot stage 120 patients (60 each for CHRONOS-A and CHRONOS-B) will be recruited from approximately 6 sites over 12-months. The pilot will assess feasibility of our recruitment timelines and final recruitment rates will be based on the data from the pilot.

The recruitment rate will be assessed as part of our pilot and timelines for the main stage will be adjusted accordingly. In order to allow the majority of UK sites to be eligible for the study, we will develop a centralised process for the delivery of trial therapies/interventions. In brief, if a site does not have direct access to either FT or radiotherapy or surgery then there will be a process in place for the treatment to take place in a nearby trial site that offers that treatment.

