8.3 Statistical analysis

Feasibility and pilot study

The primary analysis of the feasibility stage will estimate recruitment and randomisation rate to allocated arm. Safety in terms of Adverse Events will be analysed in terms of occurrence of adverse events in each arm.

The main study will be initiated if the minimum target recruitment rate of the feasibility study is within the lower end of the confidence interval and funding has been confirmed.

Main study

Time-to-event (progression or failure depending on which of CHRONOS-A or CHRONOS-B) data will be presented using Kaplan-Meier plots. In all time-to-event analyses, patients that have not experienced the event in question will be censored at the date last seen/known to be alive. The hazard ratio (HR) will be taken from a Cox proportional hazards model, adjusted for any stratification factors used at randomisation. Differences in time-to-event outcomes will be assessed using the log-rank c2 test and expressed using a hazard ratio (HR) with a 2-sided 95% confidence interval. If there is evidence of non-PH in the treatment

Protocol No: 19CX5006 v5.0 13th July 2022

Short Title: IP4 - CHRONOS	Protocol No: 19CX5006	Sponsor: Imperial College London	Version: 5.0 Date: 13 th July 2022
			13 July 2022

effect, the HRs are difficult to interpret and the restricted mean survival time (RMST) constructed from a flexible parametric model with time varying treatment effects will take primacy.

The assumption of proportional-hazards (PH) will be tested and appropriate methods applied to the data in the case of any violation. If there is no evidence of non-PH in the treatment effect, the HR for the adjusted Cox model takes primacy. If there is evidence of non-proportional hazards in the treatment effect, the HRs are difficult to interpret and the restricted mean survival time constructed from a flexible parametric model with time varying treatment effects will take primacy.

Planned interim and sub-group analyses: Each research comparison will have a pilot stage, one pre-planned interim analysis on PFS or FFS if the research comparison were to continue to a main stage study, and a final efficacy stage on PFS or FFS.

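### CHRONOS-A: the stated inputs (85% PFS, 5-point margin, alpha 0.05, 80% power) need about 246 to 250 events, not 136, and 1190 men give about 63 to 69% power

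*Protocol*

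**What the plan says.** Protocol section 8.1.2 first gives PFS "in our population at 5-years is approximately 85-90% after radiotherapy and similar for prostatectomy", then settles on one value: "it is reasonable to assume 85% PFS after radiotherapy with a non-inferiority margin of 5% for FT". The calculation repeats this, with 1:1 allocation, as "a non-inferiority margin of 0.05 with a 0.85 PFS rate in the standard care arm", and continues: "power 0.80 and alpha 0.05, drop-out after randomisation of 5%, the overall required sample size is 1190 with 136 expected total number of events". If recruitment is fast, "the power could be adjusted to 0.90 and the total sample size will be 1660 with 189 expected total number of events". No formula, hazard-ratio margin or sidedness of alpha is given.

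Section 8.3 makes the log-rank test and adjusted Cox model the analysis, with the result "expressed using a hazard ratio (HR) with a 2-sided 95% confidence interval". It states no non-inferiority criterion.

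The follow-up that generates the events is described in three ways. Section 2.7 has "At time of progression or failure judged clinically or maximum 5 years follow-up after randomisation". Section 5.9 makes 5 years the minimum per patient in the main study. Section 8.2 expects both trials to "complete recruitment within 5 years and primary outcome analysis to occur after 8 years", so the last men recruited would have 3 years. The SAP covers feasibility only. Its section 6.6.1 repeats 1190, without events or power.

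**The concern.** An event count of 136 is small for a margin of 5 points around 85%. It is also lower than 1190 men should produce at that rate under the stated timetable. If the inputs are right, the main non-inferiority comparison is short of events and its power is overstated.

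The funding case, and the steering committee's choice between 1190 and 1660 men, rest on these figures. Pilot participants are carried into the main trial. An underpowered non-inferiority trial risks missing non-inferiority for a treatment that is in fact equivalent.

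**Working it through.** **Inputs** (section 8.1.2): control PFS 0.85 at 5 years; margin 0.05, so the limit is 0.80; 1:1 allocation; alpha 0.05; power 0.80 or 0.90; drop-out 5%. Evaluable men: 1190 × 0.95 = 1130.5 and 1660 × 0.95 = 1577. Assumed here: proportional hazards, exponential PFS, true HR 1, and no contribution from drop-outs.

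**1. Margin as a hazard ratio.** ln(0.80)/ln(0.85) = 1.373, and ln(1.373) = 0.3170.

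**2. Events required.** Schoenfeld: d = 4(z_alpha + z_power)²/(ln HR)². Freedman: d = (z_alpha + z_power)² × ((1 + HR)/(1 − HR))². At one-sided 0.05 and 80% power, (1.645 + 0.842)² = 6.183. Schoenfeld gives 4 × 6.183/0.3170² = 246.1. Freedman gives 6.183 × (2.373/0.373)² = 250.2.

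| Level | Power | Schoenfeld | Freedman | Protocol |
|---|---|---|---|---|
| one-sided 0.05 | 80% | 246.1 | 250.2 | 136 |
| one-sided 0.05 | 90% | 340.8 | 346.6 | 189 |
| one-sided 0.025 | 80% | 312.4 | 317.6 | 136 |
| one-sided 0.025 | 90% | 418.2 | 425.2 | 189 |

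**3. Which level was used.** The protocol's ratios are 189/136 = 1.390 and 1660/1190 = 1.395. Moving from 80% to 90% power multiplies events by 1.385 at one-sided 0.05 and by 1.339 at one-sided 0.025. So one-sided 0.05 fits better, whereas the interval in section 8.3 corresponds to one-sided 0.025.

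**4. Attempts to reproduce 136 and 189.** Freedman at one-sided 0.05 for 90% against 85% (HR = ln 0.85/ln 0.90 = 1.5425) gives 135.8 and 188.1, which match. At a mean 5-year risk of 12.5% and 5% drop-out, however, those events need 135.8/0.125/0.95 = 1144 and 188.1/0.125/0.95 = 1584 men, not 1190 and 1660. A binary formula at 90% PFS, one-sided 0.025, gives 1190 for 80% power but 1593 for 90%. The stated 85% and 80% gave 136 under none of the formulas tried.

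**5. Events that 1190 men would produce at 85% PFS in both arms.** Hazard: −ln(0.85)/5 = 0.0325 per year. With uniform recruitment over 5 years and analysis at year 8:

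- Everyone followed for exactly 5 years: probability 0.15.
- Everyone followed to year 8: 1 − (0.85^0.6 − 0.85^1.6)/(5 × 0.0325) = 0.1628.
- Capped at 5 years: 0.6 × 0.15 + 0.4 × [1 − (0.85^0.6 − 0.85)/(2 × 0.0325)] = 0.1387.

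**6. Power.** Phi(√d/2 × 0.3170 − z_alpha). For 156.8 events: 12.52/2 × 0.3170 − 1.645 = 0.340, giving 63.3%.

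| Follow-up rule | Events, 1190 men | Power, one-sided 0.05 | Power, one-sided 0.025 | Events, 1660 men | Power, one-sided 0.05 | Power, one-sided 0.025 |
|---|---|---|---|---|---|---|
| Capped at 5 years | 156.8 | 63.3% | 51.0% | 218.7 | 75.8% | 65.0% |
| All complete 5 years | 169.6 | 66.2% | 54.1% | 236.6 | 78.6% | 68.4% |
| All followed to year 8 | 184.0 | 69.3% | 57.5% | 256.7 | 81.5% | 71.9% |
| Exactly the stated events | 136 | 58.1% | 45.6% | 189 | 70.3% | 58.7% |

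With the protocol's own recruitment (60 men in the first year, the rest over 48 months), 1190 men give 154 to 173 events and 63 to 67% power at one-sided 0.05. A simulation of 4000 trials per rule gave 62.5 to 69.2%.

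**7. Most favourable variants.** No drop-out and everyone followed to year 8: 193.7 events, 71%. A simple 5-year difference in proportions: 0.05/√(2 × 0.85 × 0.15/565) = 2.35, giving 76% at one-sided 0.05 (65% at 0.025). The same comparison with 1660 men gives 87% (79%).

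**The case against.** The strongest reply is that 136 events need not contradict 85% PFS. If recruitment ran uniformly over all 8 years, the event probability would be 0.1194, giving about 135 events in 1130 men and 188 in 1577. Sections 8.1.1 and 8.1.2 give only a combined period of 8 years. This stands as arithmetic: the number of events expected depends on the follow-up rule. But it conflicts with recruitment within 5 years in section 8.2 and with the 12 plus 48 months in the Trial Summary, and it leaves power at 58%.

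Second, a 90% control rate may have been intended and misreported. With 90% against 85%, follow-up capped at 5 years and drop-out spread over 8 years, 136 and 189 events need about 1195 and 1660 men, close to the stated figures. This is plausible but undocumented, and section 8.1.2 gives 85% twice. Nor would it rescue the power. Those events are counted at the non-inferiority limit, with the arms at 90% and 85%. If both arms truly have 90% PFS, 1130 men yield about 104 to 123 events and 72 to 78% power.

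Third, the margin is written as an absolute difference and the aim in section 1.3 is PFS at 5 years. On that scale the shortfall is about 4 points (76% against 80%). This deserves mention, but section 8.3 specifies a Cox and log-rank analysis.

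Fourth, section 8.3 does not say that the 95% interval decides non-inferiority, so the lower power figures are conditional on that.

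Finally, the main stage depends on funding, and SAP section 6.6.2 allows the sample size to be reconsidered after the pilot. That provision concerns compliance and feasibility, not this calculation. It is fair that no pilot analysis uses 136 or 189.

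**Conclusion.** The concern holds: section 8.1.2 is wrong as written. On its own inputs and the planned analysis scale, 80% power needs about 246 to 250 events at one-sided 0.05, about 1.8 times the stated 136 (246/136 = 1.81). The planned 1190 men give about 63 to 69% power, so a truly equivalent focal therapy would fail in 31 to 37% of trials. If the two-sided 95% interval decides, power is 51 to 57.5% and failure 42.5 to 49%. The 1660-man option gives about 76 to 82% at one-sided 0.05, against the stated 90%.

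The figures rest on one-sided 0.05 (inferred from the protocol's ratios, not stated), conversion of the margin to HR 1.373, exponential PFS and drop-outs contributing nothing. None of the alternatives tried, including no drop-out and the binary comparison, brings 1190 men to 80%. How 136 arose cannot be established from the documents; 90% against 85% is only an inference.

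**What to change.** In section 8.1.2, state the control PFS, hazard-ratio margin, sidedness of alpha, follow-up rule and formula, and restate both sets of events, sample size and power so that they agree. The sponsor has three options:

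- Keep 85%, the 5-point margin and 1190 men, and state the lower power under the chosen follow-up rule.
- Keep 85%, the 5-point margin and 80% power, and raise the sample size. At one-sided 0.05 this is 246.1/0.1628/0.95 = about 1590 men if all are followed to year 8, and up to 250.2/0.1387/0.95 = about 1900 if follow-up is capped at 5 years.
- State and justify a different control rate, and recompute everything for it. The 136 events cannot simply be carried over.

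Reconcile the follow-up statements in sections 2.7, 5.9 and 8.2, since they determine the event count. In section 8.3, match the confidence level to alpha and state the hazard ratio that the upper bound must exclude.

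The cost is wording in the protocol and a less favourable stated power; the correction itself adds no patients. Only the second option, or a changed control rate that raises the sample size, does so. SAP section 6.6.1 changes only if 1190 changes. This should be done before main-stage funding is sought; the pilot analysis is unaffected.
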